8.1.3 Multicenter Studies

This is a multi-center study and randomization has been stratified by site.

8.1.4 Assessment Time Windows

See Section 15.2 for the Schedule of Assessments. Assessments within the stated visit windows will be considered for analysis of the given time point. If multiple assessments occur within a visit window, the assessment occurring closest to the target day for the assessment will be used in the analysis. In the case of a tie, the worst record will be used.

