8. EFFICACY EVALUATION

8.1 Overview of Efficacy Analysis Issues

8.1.1 Handling of Dropouts or Missing Data

All reasonable efforts will be made to minimize missing data. However, there are two possibilities for data being missing. In one case, the measurement associated with an individual pocket may be missing at an evaluation. In this case, the worst previous value for this variable will be imputed for that tooth/pocket. Furthermore, the data from an entire patient may be missing because they withdrew before completing the study. For this imputation, an approach similar to that for each site will be employed. For visits that would follow a patient's premature discontinuation from the study, the worst observation associated with each individual pocket will be imputed for all subsequent visits for that patient and will thus also be carried forward for the 270-day evaluation. Subjects who drop out of the study will not be replaced.

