8.3.1 Primary Efficacy Analyses

The generalized estimating equations (GEE) method with a linear link and exchangeable covariance matrix (within subject correlation structure) will be used to estimate the treatment group effects with respect to change from baseline PD at 270 days, adjusted for baseline PD in tooth-sites with baseline PD ≥ 6 mm. The two primary hypotheses to be tested are:

- 1) The change in PD from baseline (PD ≥ 6 mm) (Screening Visit) at the 270 Day Visit differs between the Group 1 (see section 2.4) and Group 3 (placebo) treatments. Point estimates and 95% confidence intervals will be presented for the

treatment group differences in PD change from baseline at Day 270 by baseline smoker status.;

- 2) The change in PD from baseline (PD ≥ 6 mm) (Screening Visit) at the 270 Day Visit differs between the Group 2 (see section 2.4) and Group 3 (placebo) treatments. Point estimates and 95% confidence intervals will be presented for the treatment group differences in PD change from baseline at Day 270 by baseline smoker status.

SAS code for the GEE model is as follows:

```
proc gee data=Day270dataset
  where (base $\geq$ 6 and ITT Set='Y' and paramcd='PDEPTH');
  class subjid trt01a site smoker_status;
  model chg = trt01a base site smoker_status smoker_status*trt01a;
  repeated sub=subjid /type=exch;
  lsmeans trt01a/pdiff;
run;
```

Where:

- 1) The Day270dataset only includes records for Day 270 visit)
- 2) chg = change from baseline of each individual tooth site
- 3) (base \geq 6 and ittf1='Y' and paramcd='PDEPTH'): subsets the dataset to include only PD outcomes, the ITT population, and tooth sites with baseline PD greater or equal to 6mm.
- 4) chg= change in PD from baseline
- 5) trt01a = treatment group
- 6) site=investigator institution rather than tooth site
- 7) base = baseline PD

The 15-, 30-, and 60-Day visits were not included in the primary statistical model since the tooth-sites at the earlier visits may still be healing from the effects of the SRP procedure with possible SRP-related gingival swelling affecting the PD measures.

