12.2 Schedule of Events

Evaluation	Visit 1	Visit 2	Visit 3/3b	Visit 4	Treatment and Follow-up Period					
	Screening	Baseline (≤30 days from screening)	SRP (≤10 days from baseline)	Day 1 ^a (≤3 days from SRP)	Visit 5 Day 15 (±1 day)	Visit 6 Day 30 (±3 days)	Visit 7 Day 60 (±3 days)	Visit 8 Day 90 (±5 days)	Visit 9 Day 180 (±7 days)	Visit 10/EOS Day 270 (±7 days)
Informed Consent	X									
Pregnancy Test (female subjects)	X									X
Demographics	X									
Inclusion/Exclusion	X	X								
Dental History	X									
Medical History	X									
Vital Signs	X	X	X	X	X	X	X	X	X	X
Height and Weight	X ^b									X
Medical/Dental History Update ^g		X	X	X	X	X	X	X	X	X
Oral Exam	X	X	X	X	X	X	X	X	X	X
Randomization SRP ^d			X ^c							
Full Mouth Plaque Index (FMPI)		X			X	X	X	X	X	X
Clinical Measurements (PD, CAL, BOP)	X				X	X	X	X	X	X
GCF Sampling		X			X			X ^e	X ^e	X
Serum Sampling		X			X			X	X	X
Microbial Sampling		X			X			X	X	X
Radiographs		X						X		X
General Labs	X ^f							X		X
Administration of Test Article					In-office treatments as scheduled in Figure 1					
Oral Hygiene Instruction ^g	X	X	X	X	X	X	X	X	X	X
Adverse Events ^g	X	X	X	X	X	X	X	X	X	X
Concomitant Medication ^g	X	X	X	X	X	X	X	X	X	X

BOP=bleeding on probing; CAL=clinical attachment level; EOS=end of study; FMPI=full-mouth plaque index; GCF=gingival crevicular fluid; HbA1c=glycated hemoglobin; IWRS=interactive web response system; PD=pocket depth; SRP=scaling and root planing.

^a The first in-office treatment may be performed on the same day as the last SRP visit. The last SRP may occur on Visit 3/3b, or as an Unscheduled Visit. The Unscheduled Visit may be combined with Visit 4. Product administration must occur within 3 days of the last SRP visit.

^b Height is measured only at screening.

^c Randomization occurs by IWRS after SRP has been completed.

^d SRP may be initiated on the same day as the Baseline visit and may require more than one visit. Subjects with moderate to heavy deposits will typically have no more than two quadrants treated in a single SRP visit. Local anesthesia must be used for SRP.

^e Sample is collected before treatment is applied.

^f HbA1c is measured at screening only.

^g Performed at each treatment visit, as well as at each evaluation visit.

THIS PAGE HAS BEEN INTENTIONALLY LEFT BLANK

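### SAP 8.1.4 gives no route into the Day 270 analysis for a final visit outside ±7 days, so a completer's observed pocket depth may be replaced by a worst earlier value

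*SAP*

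**What the plan says.** Four parts of the SAP bear on this.

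- **Selection (8.1.4).** "Assessments within the stated visit windows will be considered for analysis of the given time point". The two sentences after it choose between several assessments inside one window (closest to target; worst if tied). Neither deals with an assessment outside every window. For the windows themselves the section says "See Section 15.2 for the Schedule of Assessments", but the SAP has no such section. The schedule is in 12.2, and its windows match protocol Table 3: Day 15 ±1, Day 30 ±3, Day 60 ±3, Day 90 ±5, Day 180 ±7, Day 270 ±7.
- **Primary dataset (8.3.1).** "The Day270dataset only includes records for Day 270 visit". The population is ITT (8.3).
- **Missing data (8.1.1).** It states that "there are two possibilities for data being missing". For a single pocket missing at an evaluation, "the worst previous value for this variable will be imputed for that tooth/pocket". For a patient who withdrew, "For visits that would follow a patient's premature discontinuation from the study, the worst observation associated with each individual pocket will be imputed" and carried to Day 270.
- **Baseline (2.2 and 12.2).** Baseline is the initial measurement. For PD, clinical attachment level (CAL) and bleeding on probing (BOP) that is the screening visit, before SRP.

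**The concern.** Scheduling windows tell sites when to book visits. Here they also decide which outcomes enter the analysis, and they leave gaps: no day from 188 to 262, and no day after 277, belongs to any time point.

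A final visit that slips past Day 277 is an ordinary event in a nine-month study. The blinded examiner still probes every pocket. If that record is not a Day 270 record, the subject stays in the ITT analysis without an observed Day 270 value, and SAP 8.1.1 offers only a worst earlier value. This is not the dropout problem, where no outcome exists. Here the outcome was measured and set aside.

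The cost would be a diluted treatment difference and a larger variance in the primary analysis. CAL and BOP at Day 270 depend on the same selection rule.

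**Working it through.** **1. The plan's own figure.** Inputs (SAP 2.6 and 3): difference 0.5 mm, SD 0.7 mm, two-sided 0.025 per comparison, power 85%.

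n = 2 × [(2.241 + 1.036) × 0.7 / 0.5]² = 42.1, so 43 per group. The noncentral t calculation gives 84.6% at 43 and 85.5% at 44, so the stated 44 reproduces. Normal-approximation power at 44: 0.5 / (0.7 × √(2/44)) = 3.350; 3.350 − 2.241 = 1.109; power 86.6%.

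**2. The windows.** 270 − 7 = 263 and 270 + 7 = 277, so Day 278 is outside by one day. The preceding window is 180 ± 7 = Days 173-187.

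**3. What the fill-in would be.** If the screening value counts as previous, the worst earlier PD is at least the baseline PD, so the imputed change is 0 or worse. SAP 8.1.1 does not say whether screening counts.

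**4. Illustration of the effect.** Assumptions not in the documents: the same share q of final visits is out of window in each arm; the imputed change is 0; the mean placebo change is −1.0 or −1.5 mm, with ST266 0.5 mm better; 44 per group.

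- Difference = 0.5 × (1 − q)
- Variance in an arm with mean change μ = (1 − q) × 0.49 + q(1 − q) × μ²

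Example with q = 5% and placebo −1.0 mm:

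- Placebo variance: 0.4655 + 0.0475 × 1.00 = 0.513
- ST266 variance: 0.4655 + 0.0475 × 2.25 = 0.572
- Pooled SD 0.737; difference 0.475
- 0.475 / (0.737 × √(2/44)) = 3.02; less 2.241 gives 0.78; power 78%

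| Out of window | Difference (mm) | Power, placebo −1.0 mm | Power, placebo −1.5 mm |
|---|---|---|---|
| 0% | 0.500 | 86.6% | 86.6% |
| 2% | 0.490 | 83% | 81% |
| 5% | 0.475 | 78% | 73% |
| 10% | 0.450 | 70% | 60% |

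**5. A milder fill-in.** Suppose only post-SRP values count as previous and the imputed change averages −0.5 mm in both arms (again an assumption). Replacing μ by μ + 0.5 in the variance gives power of 83-85% at 2%, 78-82% at 5% and 70-77% at 10%.

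These are two-sample approximations at subject level. The planned GEE model has covariates and works on tooth sites, so the figures show direction and rough size only.

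**The case against.** The strongest reply is that the SAP never orders the value to be discarded. SAP 8.1.4 does not say that in-window assessments are the only ones used, or that others are missing. SAP 8.1.1 names two kinds of missing data, and a completer probed on Day 278 is neither: the measurement exists and the patient did not withdraw. The dataset note in 8.3.1 can be read as the nominal visit. All of this stands. It means the loss is the natural consequence of the text rather than an explicit instruction. It does not remove the gap: if both readings are open, the primary dataset is not fully specified, and two programmers could build different ones.

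A reader might infer three stronger things that the documents do not support.

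- **Bias through Group 2's heavier schedule.** Twice-weekly dosing ends at three months. From Day 120 all arms share the same dosing days (protocol 7.3) and windows (protocol Table 5), and Groups 1 and 3 match throughout. Nothing points to a difference between arms in final-visit slippage.
- **Heavy data loss because the windows cover few calendar days.** Visits are booked at target days, not spread over the calendar, so coverage says nothing about the share lost.
- **A window split at the midpoint between Days 180 and 270 as the remedy.** It would open at about Day 226, before the Day 240 dose. It would also admit early-withdrawal visits, which under protocol 8.4 carry all the Day 270 assessments but which SAP 8.1.1 handles as discontinuations.

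It is also fair to say that most of the harm per affected subject comes from the worst-value rule, not from the window.

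**Conclusion.** The point holds as a gap in the analysis rule with a potentially costly default. Read as written, SAP 8.1.4 together with 8.1.1 and 8.3.1 gives an out-of-window final assessment no place in the primary analysis and leaves a worst earlier value as the only stated substitute. No other section of the protocol or SAP supplies a rule for it.

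The size cannot be fixed from the documents. It depends on an out-of-window share and a placebo change that neither document gives, and on whether screening counts as a previous value. With few visits affected, the loss of power is a few points; at 5-10% it would matter. The power loss needs no imbalance between arms, and no claim of bias is made. The sample size of 44 is not in question.

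**What to change.** Revise SAP 8.1.4 before database lock:

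1. Use the ±-day windows for reporting visit deviations, not for selecting analysis data.
2. For subjects who complete the study, take PD, CAL and BOP from the observed nominal Day 270 assessment (Visit 10), even if it falls outside ±7 days.
3. Apply the 8.1.1 imputation only when no such assessment exists, and state there whether the screening value counts as previous.
4. Keep early-termination visits under the 8.1.1 discontinuation rule.
5. Add a sensitivity analysis of the primary endpoint restricted to in-window records.
6. Correct the cross-reference from Section 15.2 to 12.2 (it also appears in 8.3.3).

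The cost is one paragraph and one derivation, with no added visits or subjects. The downside is a slightly wider spread of actual assessment days at Day 270, which the sensitivity analysis addresses. Because SAP 2.5 unblinds one statistician and one programmer at Day 90, the team that is still blinded should make the change.

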8.2 Efficacy Variables

Table 8-1 Efficacy Variables and Analysis Methods

Efficacy Variables	Method 1^a
Primary	
Pocket Depth	Δ from baseline at Day 270 in tooth-sites with baseline PD ≥ 6 mm ^a
Secondary	
Clinical Attachment Level	Δ from baseline at Day 270 in tooth-sites with baseline PD ≥ 6 mm ^a
Bleeding on Probing	Δ from baseline at Day 270 using whole mouth average percentage of site with bleeding on probing ^b

^a Generalized Estimating Equations will be used as the primary analytical method. The dependent variable will be change from baseline to Day 270 and the model will include treatment group, patients, smoking status, and investigational site for a given endpoint. A linear link and exchangeable covariance matrix will be employed. Only treatment comparisons at Day 270 will report a p-value. Comparisons at other time points will only present the point estimate and 95% confidence interval. The analyses will incorporate all data from individual tooth sites within each subject.

^b ANCOVA will be used for the analysis of this variable. The dependent variable will be change from baseline to Day 270 and the model will include treatment group, patients, smoking status, and investigational site for this endpoint. Only treatment comparisons at Day 270 will report a p-value. Comparisons at other time points will only present the point estimate and 95% confidence interval.

8.3 Analysis Methods

The Day 270 analyses will be independent of the Day 90 analyses. All primary and secondary efficacy analyses unless otherwise stated will be performed on the ITT population. Unblinding will be performed for the Primary and secondary analyses at Day 270.

8.3.1 Primary Efficacy Analyses

The generalized estimating equations (GEE) method with a linear link and exchangeable covariance matrix (within subject correlation structure) will be used to estimate the treatment group effects with respect to change from baseline PD at 270 days, adjusted for baseline PD in tooth-sites with baseline PD ≥ 6 mm. The two primary hypotheses to be tested are:

- 1) The change in PD from baseline (PD ≥ 6 mm) (Screening Visit) at the 270 Day Visit differs between the Group 1 (see section 2.4) and Group 3 (placebo) treatments. Point estimates and 95% confidence intervals will be presented for the

treatment group differences in PD change from baseline at Day 270 by baseline smoker status.;

- 2) The change in PD from baseline (PD ≥ 6 mm) (Screening Visit) at the 270 Day Visit differs between the Group 2 (see section 2.4) and Group 3 (placebo) treatments. Point estimates and 95% confidence intervals will be presented for the treatment group differences in PD change from baseline at Day 270 by baseline smoker status.

SAS code for the GEE model is as follows:

```
proc gee data=Day270dataset
  where (base $\geq$ 6 and ITT Set='Y' and paramcd='PDEPTH');
  class subjid trt01a site smoker_status;
  model chg = trt01a base site smoker_status smoker_status*trt01a;
  repeated sub=subjid /type=exch;
  lsmeans trt01a/pdiff;
run;
```

Where:

- 1) The Day270dataset only includes records for Day 270 visit)
- 2) chg = change from baseline of each individual tooth site
- 3) (base \geq 6 and ittf1='Y' and paramcd='PDEPTH'): subsets the dataset to include only PD outcomes, the ITT population, and tooth sites with baseline PD greater or equal to 6mm.
- 4) chg= change in PD from baseline
- 5) trt01a = treatment group
- 6) site=investigator institution rather than tooth site
- 7) base = baseline PD

The 15-, 30-, and 60-Day visits were not included in the primary statistical model since the tooth-sites at the earlier visits may still be healing from the effects of the SRP procedure with possible SRP-related gingival swelling affecting the PD measures.

Since there are two primary hypotheses, Bonferroni corrections will control for multiplicity with $p < 0.025$ considered significant. Point estimates and 95% confidence intervals will be presented for the treatment group differences in change from baseline at each assessment time point. These analyses will be performed once all the subjects (excluding those withdrawn) have been unblinded and completed their 270-Day Visit.

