
Duration of Treatment:
 
Group 1: ST266 dosed daily on Days 1-5, 8-12, 22, and 30, and then monthly for 7 months (Days 60, 90, 120, 150, 180, 210, and 240).
 
Group 2: ST266 dosed 2x/week (with at least one day between treatments) for the first 3 months and monthly for 5 months thereafter (Days 120, 150, 180, 210, and 240).
 
Group 3: Placebo dosed at the same frequency as Group 1.

Placebo, Dosage, and Mode of Administration: Sterile saline (0.9% NaCl) will be applied in the same manner and in the same volume as the investigational product, ST266.

Criteria for Evaluation:
 
Efficacy:
 
The primary efficacy endpoint of this study is the change from baseline in the PD for each patient at 9 months (Day 270) for those pockets ≥ 6mm at baseline.
 
Secondary efficacy endpoints of this study are:
 
(1) Change from baseline in CAL at 9 months and (2) change from baseline in BOP at 9 months for those pockets ≥ 6mm at baseline.
 
Exploratory endpoints of this study are:
 
(1) Pro-inflammatory mediators, enzymes and bone markers will be measured in gingival crevicular fluid (GCF) and serum at the baseline, Days 15, 90, 180, and 270;
 
(2) Microbial analysis of periodontal flora will be performed at baseline and at Days 15, 90, 180, and 270; and
 
(3) Change from baseline in radiographic bone levels (RBL) at Days 90 and 270. PD, CAL, BOP, and FMPI will also be summarized at Days 90, 180 and 270.
 
(4) Smoker/treatment interaction will be summarized for PD and CAL at Days 90, 180, and 270.
 
(5) Percent of patients with all pockets < 5mm will be summarized at Days 90, 180 and 270.
 
(6) Percent of patients with pockets decreasing by 2mm or more that at baseline were ≥ 5mm will be summarized at Days 90, 180 and 270.
 
(7) Percent of patients with 75% of pockets < 5mm that at baseline were ≥ 5mm will be summarized at Days 90, 180 and 270.
 
Safety: The safety endpoints are frequency and pattern of adverse events (AEs) and serious adverse events (SAEs).

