
Planned Sample Size:
 
The sample size for the study is based on the sample size required to compare treatment with ST266 versus placebo for the primary efficacy endpoint.
 
The number of subjects was estimated based on two meta-analysis studies that reviewed 50 and 72 articles respectively (Bonito, 2005).
 
Using the normal approximation for sample size determination for an independent sample t-test, and assuming a PD reduction of 0.5 mm on average (difference in means) with a standard deviation of 0.7 mm, $\alpha=0.05$ (0.025 per comparison, Bonferroni correction), and 85% power, a sample size of 44 per group will be required. The expected dropout rate is approximately 10% based on previous experiments; hence 50 subjects will be enrolled per group.

Statistical methods:
 
Analysis of the clinical efficacy data will consist of modeling endpoints, including change from

baseline in PD, CAL, BOP, and FMPI, with treatment group, smoking status, and investigational site as main effects and the interaction of smoking status and treatment group. Post-baseline treatment comparisons will be modeled through a GEE method (with a linear link and within-patient exchangeable covariance matrix), adjusting for the baseline value. Methods of analysis for periodontal flora, inflammatory cytokine levels in GCF and in serum, and RBL will be described in separate statistical analysis plans.

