2.6 Sample Size Determination

One hundred and fifty (150) subjects will be enrolled. The sample size for the study is based on the sample size required to compare treatment with ST266 versus placebo for the primary efficacy endpoint.

The number of subjects was estimated based on two meta-analysis studies that reviewed 50 and 72 articles respectively (Bonito, 2005).

Using the normal approximation for sample size determination for an independent sample t-test, and assuming a PD reduction of 0.5 mm on average (difference in means) with a standard deviation of 0.7 mm, $\alpha=0.05$ (0.025 per comparison, Bonferroni correction), and 85% power, a sample size of 44 per group will be required. The expected dropout rate is approximately 10% based on previous experiments; hence 50 subjects will be enrolled per group.

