3. GENERAL ANALYSIS AND REPORTING CONVENTIONS

For continuous endpoints, the summary statistics will generally include number of subjects with data (n), mean, standard deviation, median, minimum and maximum. No preliminary rounding will be performed; rounding will only occur after analysis. To round, the digit to right of last significant digit will be considered: if < 5 then round down, if ≥ 5 then round up. Means and medians will be presented with one more decimal place than the precision of the data. Standard deviations will be presented with two more decimal places than the precision of the data. Percentages will be presented with one decimal place. Minimums and maximums will be presented with the same precision as the original data.

For categorical endpoints, the summary statistics will generally include: number of subjects randomized and/or dosed, number of subjects with data, and the percentage of those with data in each category. Frequency distributions will be presented as appropriate.

Analysis of the clinical efficacy data will consist of modeling endpoints, including change from baseline in PD, CAL, BOP, and FMPI, with treatment group, patients, smoking status, and investigational site as main effects and adjusting for baseline values of a given endpoint. Post-baseline treatment comparisons will be modeled through a GEE method (with a linear link and exchangeable covariance matrix), adjusting for the baseline value. Methods of analysis for periodontal flora, inflammatory cytokine levels in GCF and in serum, and RBL will be described in separate statistical analysis plans.

Hypothesis testing, unless otherwise indicated, will be two-sided. When confidence intervals are presented, they will be two-sided with a confidence coefficient of 95%. Actual P-values will be reported to 3 decimal places if greater than 0.001. If less than 0.001, the value ' <0.001 ' will be reported.

The statistical software, SAS[®] version 9.3 or above, will be used for all summaries and statistical analyses.

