8.3.2 Secondary Efficacy Analyses

Additional secondary efficacy analyses will be performed to test the effects of treatment group and their interactions on the secondary endpoints of the change from baseline in CAL and BOP at Day 270. For the CAL analysis, the GEE analyses will be performed with the same statistical model as described in the primary PD efficacy analysis but with the change from baseline in CAL of tooth-sites with baseline PD ≥ 6 mm as the dependent

variable. Separate hypotheses will be performed for testing the treatment effects of group 1 versus group 3 (placebo) and group 2 versus group 3 (placebo). As described above, this model will include the baseline smoker status (smoker or non-smoker) by treatment group interaction. For the secondary efficacy analyses of the BOP change from baseline, ANCOVA will be performed with treatment group as the main effect, and covariates for baseline PD, site, patients, smoker status, and the baseline smoker status (smoker or non-smoker) by treatment group interaction. Point estimates and 95% confidence intervals will be presented for the treatment group differences in CAL and BOP change from baseline at Day 270 and by baseline smoker status.

The CAL and BOP secondary analyses described above will be tested hierarchically in the order of: CAL change from baseline at Day 270, and BOP (presented as a whole mouth average percentage) change from baseline at Day 270. The treatment effects for the CAL or BOP change from baseline at the Day 270 Visit will be compared between Treatment Group 1 and Placebo, and between Treatment Group 2 and Placebo. The alpha will be set at 0.025 to allow for the Bonferroni correction for 2 multiple comparisons for secondary endpoints. Since the smoker status by treatment group interaction is acting as a gatekeeper for further inference testing by smoker status, no additional corrections will be made for multiplicity for any additional analyses of the effects of treatment on CAL and BOP by smoker status. These analyses will be performed once all the subjects (excluding those withdrawn) completed their 270-Day Visit.

All primary and secondary analyses performed on the ITT population will be repeated using the per protocol population.

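### The primary code fits a smoking-by-treatment interaction and tests treatment with default LSMEANS, so smokers and non-smokers get equal weight and power falls when the smoking mix is uneven

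*SAP*

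**What the plan says.** The code in SAP 8.3.1 fits "model chg = trt01a base site smoker_status smoker_status*trt01a" and requests "lsmeans trt01a/pdiff". There is no observed-margins (OM) option and no ESTIMATE statement. The two hypotheses in that section are single differences, Group 1 versus placebo and Group 2 versus placebo, with estimates by smoker status to be shown as well.

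The model is described differently elsewhere in the SAP:

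- Section 2, statistical methods, includes the interaction: "with treatment group, smoking status, and investigational site as main effects and the interaction of smoking status and treatment group".
- Section 2, exploratory endpoints, lists it as something to report: "Smoker/treatment interaction will be summarized for PD and CAL at Days 90, 180, and 270".
- Section 3 leaves it out: "with treatment group, patients, smoking status, and investigational site as main effects and adjusting for baseline values of a given endpoint".
- Table 8-1, footnote a, also leaves it out: "the model will include treatment group, patients, smoking status, and investigational site for a given endpoint".
- Section 8.3.2 includes it for CAL and BOP and gives it a further role: "Since the smoker status by treatment group interaction is acting as a gatekeeper for further inference testing by smoker status".

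Section 2.6 sizes the trial as a plain two-sample comparison and concludes that "a sample size of 44 per group will be required". Randomisation is stratified by smoker status (2.5). This balances the arms within each stratum but does not fix how many smokers are enrolled. Neither document gives an expected smoker share.

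**The concern.** When a factor also appears in an interaction, default LSMEANS averages over the levels of the other class factor with equal weight. Site enters additively and cancels from a treatment difference. Smoker status does not cancel, so the printed contrast is ½ × (smoker effect) + ½ × (non-smoker effect). If one stratum is small, its imprecisely estimated effect still carries half the weight.

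Two things are at stake. With a common effect, precision is lost whenever the mix is not 50:50, although the sample size assumed no such loss. With effects that differ by smoking status, the test addresses a quantity other than the overall difference that the hypotheses describe.

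The printed LSMEANS statement also requests only treatment means. As written, the interaction reweights the primary test without producing the by-smoker estimates that the same section promises.

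**Working it through.** **Inputs.** From SAP 2.6: difference 0.5 mm, SD 0.7 mm, alpha 0.025 per comparison, power 85%, 50 enrolled per arm. Tests are two-sided (SAP 3). The primary population is ITT, with missing values imputed (8.3, 8.1.1). The share p of the smaller smoking stratum is not in the documents, so the range is shown. The result is symmetric in p, so it does not matter which stratum is the smaller.

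**The plan's own figure.** n = 2 × (0.7/0.5)² × (2.2414 + 1.0364)² = 42.1, so 43 per arm by the normal approximation. The t-test version gives 44 (power 85.5% at 44, 84.6% at 43). The stated 44 is reproduced.

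**Variance of the printed contrast.** With n per arm and the same p in each arm:

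- without the interaction: 2σ²/n
- with it: ¼[2σ²/(np) + 2σ²/(n(1-p))] = (2σ²/n) × 1/[4p(1-p)]

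A direct least-squares check at n = 50, p = 0.20 gives 0.0625σ² with the interaction and 0.0400σ² without it, a ratio of 1.56. This agrees with 1/(4 × 0.2 × 0.8).

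**Power** = Φ(0.5 / {0.7 × √(2/n) × √(1/[4p(1-p)])} − 2.2414), assuming a common 0.5 mm effect and no credit for covariate adjustment:

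| p | Variance ratio | Effective n of 50 | Power, 50 per arm | Power, 44 per arm |
|---|---|---|---|---|
| 0.50 | 1.00 | 50 | 90.8% | 86.6% |
| 0.40 | 1.04 | 48 | 89.6% | 85.1% |
| 0.35 | 1.10 | 45.5 | 87.8% | 83.0% |
| 0.30 | 1.19 | 42 | 84.9% | 79.7% |
| 0.25 | 1.33 | 37.5 | 80.3% | 74.5% |
| 0.20 | 1.56 | 32 | 73.1% | 67.0% |
| 0.15 | 1.96 | 25.5 | 62.1% | 56.0% |
| 0.10 | 2.78 | 18 | 46.1% | 40.9% |

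Without the interaction, power is 90.8% (50 per arm) or 86.6% (44 per arm) at every p.

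**Where power crosses 85%.** Set n × 4p(1-p) = 42.1. This gives p = 0.301 for n = 50 and p = 0.397 for n = 44.

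**Shift of the target.** Assume p = 0.20, an overall effect of 0.50 mm and 50 per arm, so the standard error is 0.7 × √(2/50) × 1.25 = 0.175.

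- Non-smokers 0.55, smokers 0.30: overall 0.8 × 0.55 + 0.2 × 0.30 = 0.50. The printed contrast targets (0.55 + 0.30)/2 = 0.425, with power Φ(0.425/0.175 − 2.2414) = 57%.
- Non-smokers 0.45, smokers 0.70: overall 0.50. The printed contrast targets 0.575, with power 85%.

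**Direction check.** Simulated tooth-site GEE analyses with robust standard errors (six sites, varying pocket counts, 1,000 trials per cell) gave, at 50 per arm, power of 0.886 without the interaction against 0.696 with it at p = 0.20, and 0.897 against 0.887 at p = 0.40. The levels depend on assumed variance components, so this supports the direction only. The formula carries the argument.

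**The case against.** The strongest reply is that no loss is demonstrated. Everything turns on a smoker share that the documents do not give, and at 50 per arm power stays above 85% down to a share of about 30%. The limits also depend on assumptions. If baseline and site explained 10%, 20% or 30% of the variance (assumed values), the limit would fall to about 25%, 21% or 18% at 50 per arm, and to 31%, 26% or 21% at 44. Noncentral-t calculations instead raise the limits to about 31–32% and 43–44%. The 44-per-arm case is the required number, not the ITT analysis set, so the 50-per-arm column is closer to the primary analysis. All of this stands, and it makes the size of the loss conditional.

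It can also be said that the interaction was added on purpose (document version control, version 3.2), that equal weighting is a legitimate target, and that Table 8-1 may simply be abbreviated, since footnote a omits baseline too. These points have some force. But no text adopts equal weighting as the target, and under the sizing assumptions it never improves precision.

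Finally, a main-effects GEE has its own implicit weighting when effects differ. Suppose p = 0.20, effects of 0.55 and 0.30, 15 deep pockets per smoker against 10 per non-smoker, and a within-patient correlation of 0.1 (all assumed). Its target is then about 0.493, against 0.482 under OM weighting and 0.50 by patient share. The same pocket counts would cut the variance ratio from 1.56 to about 1.42. So the choice between main effects and OM matters by 0.02 mm or less here, much less than the shift to 0.425 under equal weighting.

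**Conclusion.** The concern holds. Following the printed code exactly would produce an equal-weight average of two stratum effects as each primary test, while the hypotheses and the sample size refer to a single overall difference. On the SAP's sizing assumptions (common 0.5 mm effect, residual SD 0.7 mm, strata balanced across arms, no covariate credit), power is below the stated 85% once the smaller stratum is under about 30% at 50 per arm or 40% at 44 per arm. The loss is negligible near balance and large if one stratum is small. Under a common effect there is no bias and no change in nominal type I error from the weighting. If effects differ by smoking status, the tested quantity can move in either direction. The differing model descriptions across the SAP are a lesser, editorial matter, but they should be settled at the same time. The change is worth making before database lock because it is cheap and gives up nothing that the plan wants to report.

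**What to change.** 1. Take the two primary pocket-depth contrasts, and the two CAL contrasts, from the 8.3.1 model with `smoker_status*trt01a` removed and smoker status kept as a main effect. The LSMEANS treatment difference then does not depend on stratum weights.
2. Treat the BOP ANCOVA in the same way. No code is printed for it, so state its contrast explicitly.
3. Fit the interaction in a separate, pre-specified supportive model that supplies the by-smoker estimates and the interaction test. Reword 8.3.2 so that the gatekeeper refers to that model.
4. If the interaction must stay in the primary model, pre-specify an ESTIMATE contrast weighted by the patient-level smoker share in the ITT set. This is preferable to OM: the rows are tooth sites, so OM would weight the strata by number of deep pockets.
5. Use one model description in the six affected places: Section 2 (exploratory endpoints and statistical methods), Section 3, the Table 8-1 footnotes, 8.3.1 and 8.3.2.

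The cost is a small SAP rewording, one changed MODEL line and one extra model run, with no effect on patients or data collection. Because 2.5 describes an unblinded Day 90 analysis, record that blinded staff made the change before database lock.
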